9.3 Treatments Administered

The treatment period will consist of a first line treatment phase followed by maintenance therapy. CetuGEX™, cetuximab, 5-FU, cisplatin and carboplatin must be administered under the supervision of an investigator experienced in the use of antineoplastic medicinal products. Close monitoring is required during the infusion and for at least 1 hour after the end of the infusion. Availability of resuscitation equipment must be ensured.

Prior to the first infusion of cetuximab, patients must receive premedication with an antihistamine and dexamethasone (or another corticosteroid if dexamethasone is

contraindicated). According to the SmPC¹¹ this premedication is recommended prior to all subsequent infusions of cetuximab.

Prior to the first two infusions of CetuGEX™ (Day 0 and Day 1 of 990mg initial loading dose) patients must receive premedication consisting of paracetamol (acetaminophen) 1 g per os (PO) the evening before the infusion as well as paracetamol 1g PO, dexamethasone (or another corticosteroid if dexamethasone is contraindicated) and antihistamines approximately 60 minutes before the start of infusion. Premedication should be avoided during subsequent cycles. However, premedication might be applied after the occurrence of an IRR in relation to the previous infusion.

During administration of CetuGEX™/cetuximab, IRRs might occur. For a more detailed description of possible IRRs and dose adjustment procedures to be followed in case of IRRs, please refer to Section 9.9.

Combination Treatment Phase

Patients who fulfill all inclusion criteria and do not meet any of the exclusion criteria will be randomized in a 1:1 ratio to receive either CetuGEX™ or cetuximab in combination with 5-FU and cisplatin (or carboplatin later than the first cycle, in case of unacceptable toxicity), for a maximum of 6 chemotherapy cycles.

During the combination treatment phase, even if the chemotherapy is delayed for any reason (e.g., see Sections 9.9.3 and 9.9.4), the IMP (CetuGEX™ or cetuximab) administration may not be withheld and needs to be continued with weekly infusions as scheduled.

CetuGEX™

The study drug CetuGEX™ will be administered as infusion to all patients randomized to the CetuGEX™ arm, once weekly, starting with Day 0. Starting with the second infusion (Day 8 of Cycle 1), a time window of ± 1 day will be allowed for the weekly infusions (calculated from the previous infusion).

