10.1.2 Randomization

If the patient is eligible to participate in this study (i.e., if all inclusion criteria are met and no exclusion criteria apply), the investigator will contact the IWRS for randomization information within 1 to 3 days prior to the next scheduled visit of the corresponding patient. The patient will be randomly assigned to receive either CetuGEX™ or cetuximab by receiving a unique randomization number (as detailed in Section 9.5). The patients do not need to visit the study site for this procedure but can be informed by phone.

Additionally, the pre-existing tissue sample will be sent to the central laboratory for the following analyses:

- EGFR expression by immunohistochemistry at a central laboratory. Further immunohistochemical assessments may be performed on the tumor sample if deemed necessary by the sponsor, e.g. tissue micro arrays to further characterize the tumor.
- p16 tumor suppressor gene status, indicative for high risk of Human Papilloma Virus (HPV) in the tumor (remaining tissue needs to be stored for further analysis in case of eligibility).
- Assessment of HPV status at a central laboratory.

These analyses may be performed at a later time point during the study.

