c) If the administration of CetuGEX™ or cetuximab is skipped for any reason (see Sections 9.9.1 and 9.9.2), e.g., on Day 8, all assessments scheduled for this study visit day are to be performed as planned (i.e., including collection of blood samples for the determination of ADA and PK).

d) The platinum-based chemotherapy should be given within 24 hours after the infusion of CetuGEX™/cetuximab. Administration of 5-FU should be started within 24 hours after the infusion of CetuGEX™/cetuximab.

D = day, W = week

Day 0, Cycle 1 (Week 1)

On Day 0 of Cycle 1, eligible patients randomized to receive CetuGEX™ will visit the study site to receive their unique randomization number and perform baseline assessments as listed below and to receive a priming dose of 60 mg on this visit, after all baseline/safety assessments have been performed. The Day 0 visit is not applicable for patients randomized to receive cetuximab. General baseline assessments scheduled for Day 0 will be performed on Day 1 for those patients randomized to cetuximab.

The following assessments will be performed on Day 0 for patients in the CetuGEX™ treatment arm:

- Confirmation of inclusion/exclusion criteria.
- Physical examination.
- Vital signs (blood pressure, heart rate and body temperature), body weight and BMI.
- 12-lead ECG, if not done within 7 days prior start of study medication administration during screening phase.
- Record ECOG performance status.
- Blood and urine sampling for safety laboratory (hematology, coagulation panel, blood chemistry and urinalysis).
- Pregnancy test for female patients of childbearing potential.
- Quality of life questionnaires EORTC-QLQ-C30 and EORTC-QLQ-H&N35 (to be performed prior to any other assessments).
- Recording of concomitant medication.
- Assessment of AEs.
- Blood sampling for ADA testing.
- Blood sampling for PK assessments prior to the start of infusion and after the end of infusion.
- Blood sampling for assessment of cytokines and other relevant blood proteins (to be performed pre-dose, one hour after start of infusion and at the end of infusion).
- Blood sampling for assessment of immune status (to be performed pre-dose).
- Infusion of 60 mg CetuGEX™ priming dose.

Day 1, Cycle 1 (Week 1)

Day 1 of Cycle 1 will be the first treatment day for patients randomized to receive cetuximab. For those patients randomized to receive CetuGEX™ Day 1 of Cycle 1 should be performed within 24 hours after Day 0.

Day 1 (of each treatment cycle)

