Abbreviations: BMI = body mass index, CT = computed tomography, ECHO = echocardiogram, ECOG = Eastern Cooperative Oncology Group, EGFR = epidermal growth factor receptor, FE = Final Examination, HPV = human papilloma virus, IWRS = interactive web response system, MRI = magnetic resonance imaging, MUGA = Multiple Gated Acquisition, PK = pharmacokinetics, SCCHN = squamous cell carcinoma of the head and neck, 5-FU = 5-fluorouracil, W = week.

* Day 0 only applies for patients randomized to receive CetuGEX™.

- 1 The Safety Follow-Up Visit constitutes the Final Examination Visit for the patients treated with study medication until progression of disease.
- 2 As soon as progression of disease is detected, FE assessments will be performed for all patients who prematurely discontinued study treatment. For patients withdrawing prematurely from the complete study, the Final Examination will be performed at the date of withdrawal.
- 3 Will be performed quarterly by phone calls for at least 24 months after randomization of last patient.
- 4 To be performed pre-dose, as applicable.
- 5 To be performed only for patients receiving cetuximab, only on Day 1 of Cycle 1.
- 6 The investigator may contact the IWRS for randomization within 1 to 3 days prior to first infusion.

- 7 To be performed in Cycle 2 and every following cycle; To be performed in Cycle 1 only for patients receiving cetuximab.
- 8 Height will be measured only at screening.
- 9 Only to be performed, if not done within 7 days prior randomization.
- 10 To be performed every 6 weeks after randomization (i.e., Day 1 of Cycles 3 and 5, and every 6 weeks thereafter).
- 11 To be performed every 6 weeks within the first 18 weeks after randomization, and every 8 weeks thereafter.
- 12 To be performed every 6 weeks after randomization.
- 13 Pre-existing tumor-tissue samples will be sent to laboratory once patient was randomized; remaining tumor-tissue needs to be stored for further analysis
- 14 To be performed only in a subset of approximately 30 patients per treatment arm.
- 15 To be performed pre-dose, 1h after start of infusion and at the end of the first infusion.
- 16 To be performed pre-dose, at the start of the highest infusion rate, 1 h after start of the highest infusion rate and at the end of infusion on Day 1 of Cycle 1; pre-dose, 1 h after start of infusion and at the end of infusion on Day 1 of Cycle 2.

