Variable Name	Computation Methods, Notes, or Equation(s)		
PFSp  (primary definition)	= Earliest date of progression or death - date of randomization + 1 The earliest date of PD will be used irrespective of PD confirmation		
	Finding	Date of PD of Censoring	Outcome
	No PD or death	Pre and post-baseline imaging done: Date of last imaging	Censored
		No baseline or no post-baseline imaging done: Date of randomization	Censored
	Progression/death documented after a new anticancer treatment has started PD at scheduled visit PD between scheduled visits	Date of last imaging prior to new anticancer treatment Date of imaging Date of imaging	Censored Event Event
PFSs  (sensitivity definition)	= Earliest date of progression or death - date of randomization + 1 The earliest date of PD will be used irrespective of PD confirmation		
	Finding	Date of PD of Censoring	Outcome
	No PD or death	Pre and post-baseline imaging done: Date of last imaging	Censored
		No baseline or no post-baseline imaging done: Date of randomization	Censored
	Progression/death documented after a new anticancer treatment has started PD at scheduled visit PD between scheduled visits*	Date of last imaging prior to new anticancer treatment. Date of imaging Date of next scheduled visit	Censored Event Event
	PD after 2 or more missing scheduled visits	Date of last imaging prior to first missing visit.	Censored
	Death up to 16 weeks (112 days) after last imaging Death later than 16 weeks (112 days) after last imaging	Date of death Date of last imaging	Event Censored
Best overall response	Best modified irRC classification (CR, PR or SD) as assessed by the investigator or by the independent centralized review		

(rates) (BO(R))	SD: follow-up measurements must have met the SD criteria at least once after randomization at a minimum interval of 8 weeks.
Objective response (rate) (OR(R))	Best response of CR or PR
Clinical benefit (rate) (CB(R))	Best response of CR or PR or SD. SD: follow-up measurements must have met the SD criteria at least once after randomization at a minimum interval of 8 weeks

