\* Scheduled visits are expected to be performed every 6 weeks after day of randomization until Week 18 and every 8 weeks thereafter. An assessment is considered “between scheduled visits” if it is performed more than 7 days before the next scheduled visit.

The following variable will be derived with respect to hospitalization:

Variable Name	Computation Methods, Notes, or Equation(s)
Percentage of days in hospital	(Number of days of hospitalization (sum of all: discharge date [or death date if died in hospital] – admission date +1) divided by number of days from randomization to EOS visit) * 100%

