### 9.1 Primary Efficacy Analysis

The primary efficacy analysis for PFS as assessed by the investigator will be based on the ITT population using the PFSp definition as described in Section 7.2.

A two-sided log-rank test will be used to test the null hypothesis of equal treatment effects at an overall significance level of 0.05. The Kaplan-Meier method will be used to estimate the survival functions. Median survival times together with their 95%-confidence intervals will be retrieved from the survival functions. PFS rates at 6, 12, 15 and 18 months and associated 95%-confidence intervals and graphs of the Kaplan-Meier curves by treatment arm will also be presented.

The primary efficacy analysis will not be stratified by the factors used for stratification at randomization in order to preserve the estimated power considering the high number of strata.

To investigate the influence of the stratification factor on the primary endpoint a Cox regression model will be applied as a sensitivity analysis based on the ITT population. This model will include the treatment effect and the stratification factors

- FcγRIIIa allotypes (FF, FV or VV)
- Oral cavity and oropharynx vs. other locations
- Locally recurrent vs. metastatic disease
- EGFR treatment naïve vs. EGFR treatment as part of multimodal treatment

The hazard ratios, the corresponding 95% confidence intervals and the p-values of the Wald test (using adjustment for ties according to Efron) will be presented for all factors. The Kaplan-Meier analyzes will be repeated separately within the subgroups formed by the stratification factors. Corresponding figures will combine the curves for all treatment group/factor level combinations on one page per factor. Factor levels maybe combined if the sample size per level is  $< 15$ .

Further sensitivity analyses will be done as follows

- The analyses will be repeated using the PFSs definition as described in Section 7.2
- The analyses will be repeated for the PP Population
- It has been recognized that not all sites had strictly applied modified irRC for response assessment. To investigate the influence of deviating response criteria on PFS a log rank test will performed stratifying sites according to strict adherence to modified irRC (yes/no).

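### The PFSs footnote gives no tolerance after a scheduled visit, so a progression seen on a scan one day late is re-dated by 41 or 55 days

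*SAP*

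**What the plan says.** SAP 7.2 defines two versions of PFS. PFSp, the primary one, dates every progression by its imaging date. PFSs differs for a progression found between scheduled visits: it is still an event, but its date becomes "Date of next scheduled visit".

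The footnote to the table places scheduled visits every 6 weeks from randomization to week 18 and every 8 weeks after that. It counts an assessment as between visits "if it is performed more than 7 days before the next scheduled visit". It sets no condition on the time since the preceding visit.

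PFSs is used in SAP 9.1: "The analyses will be repeated using the PFSs definition as described in Section 7.2". Those analyses include Kaplan-Meier medians and "PFS rates at 6, 12, 15 and 18 months and associated 95%-confidence intervals". The table list in SAP 15.1 also plans PFSs tables for both central reads (14.2.2.7, 14.2.2.8, 14.2.3.7 and 14.2.3.8).

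On scan timing, footnote 10 of the Schedule of Events (Protocol 18.1) says "To be performed every 6 weeks after randomization (i.e., Day 1 of Cycles 3 and 5, and every 6 weeks thereafter". Protocol 10.1.2 says that "the investigator will contact the IWRS for randomization information within 1 to 3 days prior to the next scheduled visit". Neither document gives an imaging window. Protocol 9.3 gives a tolerance of one day either way for infusions only, counted from the previous infusion, so drift can accumulate.

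**The concern.** A rule for scans between visits should catch scans that are far from any scheduled visit. This one also catches a scan one day after a visit, because that scan is almost a whole interval away from the next one. Only progressions are moved; scans without progression keep their dates. Read as written, PFSs therefore lengthens PFS for ordinary late scans, and its medians and rates can exceed those of PFSp for a reason unrelated to disease or treatment.

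PFSs exists to show whether the primary result is robust to assessment timing. A PFSs median that moves because of a gap in the drafting gives a misleading answer. Two competent programmers could also get different results, one from the footnote and one from nominal visits.

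**Working it through.** **Plan's own figures.** The documents give no figure for the re-dating shift. The design inputs used below (medians 5.6 and 8.4 months, two-sided 5%, 80% power, SAP 5) do reproduce the plan. Schoenfeld's formula gives 4 × (1.960 + 0.842)² / [ln(5.6/8.4)]² = 191 events, against 192 stated. With 24 months of accrual, 12 months of further follow-up and 10% drop-out, 240 patients give about 194 events.

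**1. Size of the shift.** The SAP 7.2 schedule falls on days 42, 84 and 126, then every 56 days (182, 238, 294, 350, 406, 462, 518, 574).

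| PD scan | PFSs date | Shift |
|---|---|---|
| day 43 | day 84 | 84 − 43 = 41 |
| day 85 | day 126 | 126 − 85 = 41 |
| day 127 | day 182 | 182 − 127 = 55 |
| day 49 (7 days late) | day 84 | 35 |
| day 133 (7 days late) | day 182 | 49 |
| day 35 to 41 (early) | unchanged | 0 |

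**2. Planned rate times.** PFS in months = (day + 1)/30.4375. A PD scan one day late moves as follows:
- day 127: 128/30.4375 = 4.21 becomes 183/30.4375 = 6.01, past 6 months
- day 351: 11.56 becomes 407/30.4375 = 13.37, past 12
- day 407: 13.40 becomes 463/30.4375 = 15.21, past 15
- day 519: 17.08 becomes 575/30.4375 = 18.89, past 18

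All four planned rates can be affected.

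**3. How likely lateness is at weeks 6 and 12.** Cycle 3 Day 1 is 42 days after Cycle 1 Day 1. Randomization is 1 to 3 days before the first infusion. For CetuGEX the first infusion is on Day 0, and "Day 1 of Cycle 1 should be performed within 24 hours after Day 0". Nominally, Cycle 3 Day 1 is therefore day 43–45 (cetuximab) or 44–46 (CetuGEX). Six weekly steps of ±1 day widen this to day 37–51 or 38–52, so not every scan is late.

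Assume that each step is −1, 0 or +1 day with equal chance and that the randomization gaps of 1, 2 and 3 days are equally likely. For cetuximab, Cycle 3 Day 1 is then after day 42 with probability (435 + 561 + 651)/(3 × 729) = 75.3%. For CetuGEX it is (561 + 651 + 701)/(3 × 729) = 87.5%. The same calculation with 12 steps puts Cycle 5 Day 1 after day 84 in 69% and 80%. From week 18, imaging is timed from randomization (Protocol 10.1.4), so those scans are late only through ordinary scheduling slip.

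**4. Effect on PFSs (simulation).** Settings: 120 patients per arm, exponential latent medians 5.6 and 8.4 months, 24-month accrual, cut-off at 36 months, 10% drop-out over 24 months, and 12% of events being deaths (assumed). Medians are averages over simulated trials.

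*Only week 6 and 12 scans off schedule.* 24% (control) and 22% (CetuGEX) of progressions are re-dated, by about 39 days on average. HR is 0.663 for PFSp and 0.662 for PFSs. Medians and 6- to 18-month rates do not change.

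*Week 18 and later scans also spread evenly over ±3 days (assumed).* About 54% of progressions are re-dated, by about 48 days:

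| | Control PFSp → PFSs | CetuGEX PFSp → PFSs |
|---|---|---|
| Median, months | 6.5 → 7.2 | 9.2 → 9.9 |
| 6-month PFS | 54.1% → 58.2% | 66.2% → 69.3% |
| 12-month PFS | 24.0% → 26.3% | 38.6% → 41.0% |

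HR is 0.663 against 0.664. Rejection under the null is 4.9% for both definitions.

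*No true effect, lateness unequal (assumed), CetuGEX later.* With 45% against 55% late, HR goes from 0.995 to 0.979 and rejection from 4.5% to 5.0%. With 40% against 60% late, HR goes from 0.986 to 0.954 and rejection from 5.0% to 6.6%.

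**5. With a two-sided 7-day window.** In the two scenarios with a true effect, under 1% of progressions are re-dated, and medians and rates equal those of PFSp.

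**The case against.** The strongest reply is that a scan on Cycle 3 Day 1 simply is the scheduled visit. The Schedule of Events equates 6 weeks after randomization with that cycle day, Protocol 10.3.2 does the same for the quality-of-life visits, and the PFSs table has a separate row for progression at a scheduled visit, dated by imaging. On that reading nothing is re-dated. It is a reasonable reading, but the SAP does not state it, and the only written test is the one-sided footnote.

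It is also true that only a sensitivity analysis is touched. The treatment comparison is essentially unchanged when lateness is similar in the arms. The lateness built into the dosing schedule changes no planned median or rate by itself; the inflation needs slip at week 18 and later, and the documents do not say how much there will be. The size depends on the model. A second simulation in which every event is a progression and half of all scans are 1 to 3 days late moves control 6-month PFS from 59.9% to 65.4%. With 10% late, medians do not move and the 6-month rate rises by about 1 point. In the unequal-lateness cases, only the 20-point imbalance raises rejection clearly above 5%; with 2,500 simulated trials the standard error is about 0.4 points.

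Finally, a 7-day window does not remove the jump. The infusion tolerance allows Cycle 3 Day 1 as late as day 51 or 52, and a progression on day 50 would still move to day 84, a shift of 34 days. This is rare under the drift assumed above.

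**Conclusion.** The concern holds and should be fixed. Applied as written, the footnote re-dates a progression on a scan one day late by 41 or 55 days while leaving a scan up to 7 days early alone. The shifts follow directly from the SAP's own schedule and need no assumption.

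The effect on results does rest on assumptions about scan timing. It ranges from none on medians and rates (only week 6 and 12 scans off schedule) to about 0.7 months on each median and 3 to 4 points on 6-month PFS (later scans also within ±3 days). The hazard ratio and log-rank test are biased only if lateness differs between arms. PFSp, the primary test and the 192-event calculation are unaffected.

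**What to change.** Before database lock, amend the footnote in SAP 7.2: an assessment is between scheduled visits only if it is more than 7 days after the preceding scheduled visit and also more than 7 days before the next one. Scans within 7 days either side of a scheduled visit keep their imaging date. The 7 days after a visit mirrors the SAP's existing 7 days before.

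If the sponsor intends nominal visits, the same sentence should add that a scan done for Day 1 of Cycle 3 or 5 counts as the week 6 or week 12 visit. That would also cover the few such scans more than 7 days late.

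The cost is one sentence in the SAP and one line of derivation code. No data collection changes, and the rule for true interim scans stays.

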## 8. STUDY PATIENTS AND DEMOGRAPHICS

### 8.1 Disposition of Patients and Withdrawals

All patients who provide informed consent will be accounted for in this study.

Descriptive summaries of population data will include

- the frequency and percentage of patients in each study population, overall and by center
- the disposition of patients, including number of patients who gave informed consent for screening, number of screening failures, number of patients randomized, number of patients completing the clinical phase (EOS visit after observed progression), number of patients discontinuing treatment without preceding progression, reason for discontinuation from treatment
- study withdrawals by reason of withdrawal
- the frequency and percentage of patients in cross-sectional subgroups defined by the stratification factors at randomization
  - FcγRIIIa status (FF, FV or VV)
  - Oral cavity and oropharynx vs. other locations
  - Locally recurrent vs. metastatic disease
  - EGFR treatment naïve vs. EGFR treatment as part of multimodal therapy

and will be presented for all randomized patients, unless otherwise specified. Subgroups will also be detailed for the PP population.

### 8.2 Protocol Violations and Deviations

Clinical data will be checked for potential protocol violations before database lock in order to define the analysis populations. A data review meeting will be held after database soft lock. Cases and frequency of patients violating the criteria listed below will be analyzed and categorized as minor or major protocol violations. Patients with one or

more major protocol violation will be excluded from the PP population, patients with only minor or no violations will be included.

Violations of the following criteria may constitute a major protocol violation. Final decisions will however be made at a blinded data review meeting prior to data base lock:

- histologically confirmed recurrent and/or metastatic SCCHN not eligible for local treatment
- measurable disease according to RECIST 1.1
- at least 18 years of age at screening
- Eastern Cooperative Oncology Group (ECOG) at Screening  $\leq$  1
- negative pregnancy test at screening/prior to randomization (if female and of childbearing potential)
- no clinical evidence of brain metastasis or leptomeningeal involvement
- no nasopharyngeal tumors
- no myocardial infarction within 6 months prior to screening
- no symptomatic congestive heart failure (NYHA Grade 3 or 4), no unstable angina pectoris within 6 months prior to screening, no significant cardiac arrhythmia, no history of stroke or transient ischemic attack within 1 year prior to screening
- no prior allergic reaction to a monoclonal antibody, no grade 3 IRR or any grade 4 reaction to a monoclonal antibody
- no pregnancy during study
- treatment as randomized

Other issues which become obvious during data review may be considered as potential major violations as well.

Furthermore, data listings will be reviewed for prohibited previous and concomitant therapies (as defined in protocol sections 8.2.2 and 9.12.2).

Major and minor protocol violations will be summarized by type of violation and by treatment group for the ITT population. Individual patients with major protocol deviations will be listed.

